3.3 Sample Population

The Bajau adults are considered as a high-risk individuals alongside Indians, Orang Asli and other indigenous communities in Sarawak and Sabah (OHD, 2018). A high-risk population is defined as communities that practices risk habits such as smoking, drinking alcohol and chewing BQ or living in a community which favours the tendency to take up those habits (OHD, 2002).

Table 3.3 shows that Bajau was the most dominant ethnic group that practiced BQ chewing habit in Kota Belud for the past two consecutive years compared to other races. Data was retrieved from Kota Belud’s District Dental Office oral cancer screening report.

Table 3.3 Local District Screening Report of Ethnic Distribution of BQ Chewers in Kota Belud for 2021-2022

Ethnic	2021	2022
Bajau	307	226
Dusun	300	163
Bumiputera Sabah Lain	97	71

Tentatively, a total of 6 villages will be selected for the conduct of this study; 1 village for pre-test, 1 village for pilot test and another 4 villages for the implementation of the study (2 villages for intervention study and 2 villages for the control arm).

3.4 Sample Size

The sample size needed for this study will be calculated from a previous study performed by Herzog TA et al. (2022). The sample size was calculated using OpenEpi Version 3 software with the following assumptions:

 Margin of error (α error)	:	0.05
 Power of study ($1-\beta$)	:	0.8
 Allocation Ratio	:	1
 Percent of Exposed with Outcome	:	38.64 %
 Percent of Unexposed with Outcome	:	9.09 %

A total of 76 participants are needed for this study and 38 participants in each arm. After calculation of 20% dropout at 22th day and in 3 months (16 people), a revised total of 92 participants are needed for this study with 46 participants in each arm (Figure 3.1)

[figure not shown]

[figure not shown]
Figure 3.1 Flow of the Participant Allocation in the Study

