intervention can be used by targetting the adverse effects of AN and as well to promote cessation (Little MA & Papke RL, 2015). They too proposed since **cognitive-behavioral therapy** is widely used to assist people to stop smoking, a similar behavioural therapy will be helpful and would possess as a good starting point for the development of AN cessation interventions. Since Moss J. et al. (2015) developed a BQ cognitive behavioural cessation program specially for BQ chewers in the islands of Guam and the intervention has **yielded a high self-reported cessation rate (65%)**, efforts can be directed to adapt the program to the Malaysian high risk communities. After a period of adaptation, this program can be extended to medical counterparts for training and implementation accordingly in their related fields. Since the original study mainly conducted the **intervention as group-based**, it is very advantageous to Malaysian high risk communities as the BQ chewing habits here are culturally-linked and community-based. Apart from that, Shirzaiy M et al. (2020) too emphasized the **most important treatment modality for BQ chewers with oral submucosal fibrosis is cessation and education programs**. He further claimed without habit cessation, the OSF condition has a high possibility for a malignant transformation. Maling TH et al. in 2016 conducted a quasi-experimental study using a structured Oral Health Educational module based on Health Belief theory to intervene a high risk community in Limbang, Sarawak. After the structured educational program, there was a significant drop in the number of current BQ chewers (17.6% at 1-month and 23.5% at 3-month post intervention). In the aspect of frequency of BQ chewing, there was a drastic drop in the daily chewing section (66.7% at 1-month and 88.9% at 3-month post intervention). In the aspect of commitment to quit habit, more than half stated will reduce or modify their habit after attending the educational program (66.7% at 1-month and 58.3% at 3-month post intervention). Thus, this further proves that a structured educational program is very crucial in tackling conditions with high risk behaviours that involves closely with addiction or dependency syndrome.

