3.0 MATERIALS AND METHOD

3.1 Overview of the Study design

This is a comparative prospective community trial which utilises a cluster randomised controlled trial design involving a Bajau indigenous community in Sabah, Malaysia with a 1:1 allocation ratio. The clusters are Bajau villages that practises BQ chewing habits in Kota Belud district in Sabah. The Bajau villages are the unit of randomisation. There are 39 Bajau villages in Kota Belud, Sabah (Tahir Z et al., 2003).

The clustered randomised controlled trial study design was selected as there was a high tendency of crossover if both intervention and control groups are randomised within the same village. Individuals allocated to a control group may inadvertently receive some aspects of the intervention if they are in proximity to the individuals in intervention group (Hahn S et al (2005). Thus, clustered randomised trial is the best available design for researchers who evaluating intervention that operates at group level, that manipulates the social and physical environment and cannot be delivered to individual participants without any substantial risk of contamination (NIH, 2022).

The eligible villages will be randomised into intervention and control groups based on the required sample size. The intervention group will receive an educational booklet and a structured BQ cessation program which will be cross- culturally adapted first based on a clinical trial (BENIT) by Paulino YC et al. (2020) for a Malaysian high risk population. The control group will only receive an educational booklet.

Baseline information on participant's demographics, BQ chewing behaviours, BQ composition, BQ dependency levels, reasons for chewing, the readiness and self perceived barriers to cease habit will be obtained prior to the commencement of the intervention. The

same participants will be followed-up at 22-day and 3-month after commencement of intervention to assess their of quitting experience and impact of the intervention. Day 22 follow-up was kept in this study as it will enable study results to be compared with similar BQ cessation studies in other parts of the world such as in Pacific Islands (Moss J. et al., 2015 and Paulino YC et al., 2020).

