3.5 Sampling and randomisation method

Prior to randomisation, matching of eligible Bajau villages will be carried out to increase precision and to minimise imbalance across intervention and control groups. This study involves 2 levels of randomisation. The randomisation sequence will be carried out by statistician employed at Faculty of Dentistry, Universiti Malaya.

At the first level of randomisation, all eligible Bajau villages from the total 39 Bajau villages will be paired according to location and average number of BQ chewers in the village (Figure 3.2).

At the second level of randomisation, computer generated random numbers will be used to randomly allocate the Bajau villages in each matched-pair to intervention and control groups. The match-pairs will be randomly selected until the sample size is met.

Bajau villages matched according to average number of BQ chewers in the village

Figure 3.2 Diagram depicting Flow of Matching of Clusters in the Study

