3.6 Allocation concealment

In this study, allocation concealment will be done at cluster level. A senior dental officer (SDO) in Kota Belud Dental District Office who is not involved in cluster identification and recruitment will keep the allocation sequence in a brown envelope in his or her SDO's office until the matched pair are ready to be recruited into the study.

The allocation sequence will be generated by a statistician employed at the Faculty of Dentistry, Universiti Malaya using computer generated tables. The information will be kept confidential until the intervention are assigned to the villages.

Within the cluster, a universal sampling technique will be used to recruit participants into the study. Universal sampling is also known as a total population sampling; which is a type of purposive sampling that involves examining the entire population that have a particular set of characteristics (Laerd Statistics, 2012). All eligible participants who fulfilled the inclusion and exclusion criteria through the screening session will be recruited as study sample. Thereafter, informed consent will be obtained from the participants.

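### The 80% power in section 3.4 is computed for independent individuals, although the trial randomises matched villages, tentatively two per arm

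*Protocol*

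**What the plan says.** Protocol section 3.4 lists alpha 0.05, power 0.8, allocation ratio 1, and outcome percentages of 38.64% and 9.09%, entered in OpenEpi. The result is: "A total of 76 participants are needed for this study and 38 participants in each arm". The only inflation, from 76 to 92, is attributed to 20% dropout.

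The design sections describe a different kind of trial. Section 3.1 states: "The Bajau villages are the unit of randomisation". Section 3.3 says: "Tentatively, a total of 6 villages will be selected for the conduct of this study", of which one is for the pre-test, one for the pilot and "another 4 villages for the implementation of the study (2 villages for intervention study and 2 villages for the control arm". Section 3.5 uses random numbers to "randomly allocate the Bajau villages in each matched-pair to intervention and control groups", and adds: "The match-pairs will be randomly selected until the sample size is met". Within each village, section 3.6 says that "a universal sampling technique will be used to recruit participants into the study".

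**The concern.** When whole villages are randomised, people in the same village tend to have similar outcomes, so each person adds less information than an independently randomised one. The number of villages also limits the degrees of freedom for the between-arm comparison. A calculation that ignores both overstates power.

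The protocol gives its own reasons to expect correlation. Section 1.4 says that "BQ chewing habits here are culturally-linked and community-based", and section 3.10.3.1 advises chewers to come with relatives or neighbours who also chew. Section 3.1 chose cluster randomisation because people living close together could share the intervention.

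The hypothesis in section 1.7 is a between-arm difference in cessation at 3 months. If 80% power is claimed but not delivered, a non-significant result would be read as stronger evidence against the programme than it is. If the analysis also ignored villages, the false-positive rate would exceed 5%. That second risk is conditional, because the protocol names no between-arm test.

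**Working it through.** **1. Reproduce the protocol's figure.** Inputs from section 3.4: p1 = 0.3864, p2 = 0.0909, difference d = 0.2955, mean p = 0.23865, two-sided alpha 0.05 (z = 1.960), power 0.80 (z = 0.842). Section 3.4 does not state sidedness; the two-sided reading is the one that returns 38.

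- Uncorrected: n = [1.960·√(2 × 0.23865 × 0.76135) + 0.842·√(0.3864 × 0.6136 + 0.0909 × 0.9091)]² / 0.2955² = [1.960·√0.3634 + 0.842·√0.3197]² / 0.2955² = 31.46.
- Continuity-corrected: n/4 × [1 + √(1 + 4/(n·d))]² = 37.92, rounded up to 38.

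This matches section 3.4. The formula has no cluster term, so 76 corresponds to a design effect of 1.

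**2. Apply a design effect.** Assumed: 38 completers per arm in two villages of m = 19, and ICC from 0.01 to 0.10 (the protocol gives none). DE = 1 + (19 − 1) × ICC; effective n = 38/DE. The type I error column is 2 × [1 − Φ(1.96/√DE)], for an uncorrected z test that ignores villages.

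| ICC | DE | Effective n per arm | Power, continuity-corrected | Power, uncorrected | Type I error if villages ignored |
|---|---|---|---|---|---|
| 0 | 1.00 | 38.0 | 80% | 87% | 5% |
| 0.01 | 1.18 | 32.2 | 71% | 81% | 7% |
| 0.02 | 1.36 | 27.9 | 63% | 75% | 9% |
| 0.05 | 1.90 | 20.0 | 44% | 60% | 16% |
| 0.10 | 2.80 | 13.6 | 26% | 43% | 24% |

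**3. Account for the number of villages.** Power of a two-sided 5% t test on village cessation proportions, from beta-binomial simulation with 200,000 runs per cell. The range runs from ICC 0 to ICC 0.10.

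| Villages per arm × completers | Matching ignored | Matching respected |
|---|---|---|
| 2 × 19 | 44% to 25% (2 df) | 20% to 13% (1 df) |
| 4 × 10 | 79% to 53% (6 df) | 61% to 38% (3 df) |
| 8 × 5 | 86% to 74% (14 df) | 81% to 68% (7 df) |

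A noncentral-t approximation for 2 × 19 agrees: 43% to 21% with 2 df and 20% to 12% with 1 df. The matched figures assume no precision gain from matching, because no matching correlation is given. The matched 2 × 19 figures also count identical pair differences (zero estimated variance) as significant; without that they are 9% to 6%.

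**4. Two limits of two villages per arm.** Two matched pairs allow 2² = 4 allocations, so an exact two-sided randomisation test cannot give p below 2/4 = 0.5. With the village count fixed at two per arm, even the design-effect calculation cannot reach the required 38 effective participants per arm once the ICC is 2/38 = 0.053 or more, however many people each village supplies.

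**The case against.** The strongest reply is that two villages per arm is only tentative and that section 3.5 adds pairs as needed. Section 3.3 reports 307 Bajau chewers screened in the district in 2021 and 226 in 2022. Spread over 39 Bajau villages, that is about 6 to 8 each, so 92 participants might need some 12 to 16 villages, or 6 to 8 per arm. At 8 villages of 5 per arm the loss is modest: power is about 84% unmatched and 79% matched at ICC 0.02.

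This stands as a limit on the size. The two-per-arm figures hold only if the tentative plan holds, and screening counts are not a census, so villages may contain more chewers than this. It does not rescue section 3.4. The rule in section 3.5 stops at an unadjusted total, so the protocol secures neither a village count nor a cluster-adjusted target.

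Two further points are fair. Part of the fall to 71% at ICC 0.01 reflects the conservative continuity correction; the uncorrected formula gives 81% there. The evidence for correlation concerns the habit and attendance, not quitting itself, so it makes an ICC plausible without sizing it.

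Matching may recover some precision, as section 3.5 intends, but section 3.4 takes no credit for it and two pairs leave one degree of freedom. A separate analysis plan could specify a clustered analysis, but it would not make the power stated in section 3.4 correct.

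**Conclusion.** The concern holds. The 76 participants in section 3.4 come from a formula for independent individuals, and the 80% power attached to them is not what a village-randomised trial of this size delivers.

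That conclusion needs no assumed ICC at the tentative village count: with two villages per arm, village-level power is about 44% unmatched or 20% matched even at ICC 0. How large the shortfall finally is depends on the ICC and the number of villages, neither of which the protocol fixes. At four villages per arm, power stays below 80% throughout the range examined. At eight it is near or above 80% for small ICCs and falls to 74% unmatched or 68% matched at 0.10. The type I error figures apply only if the analysis ignores villages.

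**What to change.** In section 3.4, replace the 80% power statement with the power of the village-randomised design. State the assumed ICC range, the resulting design effect, the number of villages per arm, and whether the degrees of freedom are matched or unmatched. If only about two villages per arm are kept, describe the between-arm cessation comparison as exploratory. These changes cost wording only, though the power figure will be less favourable.

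The stopping rule in section 3.5 should refer to a cluster-adjusted target, not the unadjusted 76 (92 with dropout). On the design effect alone, with 19 completers per village, the analysed total 2 × 38 × DE (rounded up within each arm) is 90, 104, 146 or 214 for ICC 0.01, 0.02, 0.05 or 0.10, before any allowance for few villages. Meeting such a target means more screening days, sessions and follow-up visits within the July to September field window in section 3.25. Whether to enlarge the trial is the sponsor's choice; correcting the power statement does not depend on it.

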3.9 Participant/Subject Withdrawal Criteria

The Main Researcher may withdraw (remove) a participant from some study components at her discretion if participant is non-compliant with required study regimens or procedures.

A participant can voluntarily withdraw from participation in some or all components of a study for which he or she has previously consented if he or she has a valid reason. Withdrawn participants will be replaced only if required sample size is not fulfilled.

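### The planned 92 participants cover a 17.4% dropout, not the stated 20%, because 20% of 76 was added instead of dividing 76 by 0.8

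*Protocol*

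**What the plan says.** Section 3.4 (Sample Size) sets a 5% error rate, 80% power, equal allocation, and cessation rates of 38.64% under intervention and 9.09% under control. From these it concludes: "A total of 76 participants are needed for this study and 38 participants in each arm". It then makes the allowance for losses: "After calculation of 20% dropout at 22th day and in 3 months (16 people), a revised total of 92 participants", which it splits as 46 per arm.

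Two later provisions lean on this figure. Section 3.5 uses it to end the selection of village pairs: "The match-pairs will be randomly selected until the sample size is met". Section 3.9 uses it to decide on replacement: "Withdrawn participants will be replaced only if required sample size is not fulfilled".

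**The concern.** The percentage and the enrolment figure in one sentence do not agree. A dropout rate is a fraction of the people enrolled, so the number to enrol is the number needed at the end divided by one minus that rate. The protocol instead took 20% of the number needed at the end and added it. This always gives too few, and here it leaves the evaluable number below the protocol's own minimum if the assumed dropout occurs.

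The 38 per arm has almost no slack, since the unrounded requirement is 37.9. In addition, section 3.15.2 restricts the cessation analysis to participants who attended all sessions, so losses reduce the analysed number directly. The figure also serves as a target in sections 3.5 and 3.9, and an error in it moves the point at which those rules are satisfied.

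**Working it through.** **Inputs, all from section 3.4:** p1 = 0.3864, p2 = 0.0909, alpha = 0.05, power = 0.80, ratio 1:1, evaluable N = 76 (38 per arm), dropout 20% entered as 16 people, enrolled N = 92 (46 per arm). The protocol does not say whether alpha is one- or two-sided; two-sided is assumed because it reproduces the stated number.

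**1. Reproducing the 76.** Let d = p1 − p2 = 0.2955 and let p̄ = 0.23865 be the mean rate.

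- Without continuity correction: n0 = [1.96·√(2p̄(1−p̄)) + 0.8416·√(p1(1−p1) + p2(1−p2))]² / d² = 31.46, so 32 per arm.
- With continuity correction: n = (n0/4)·[1 + √(1 + 4/(n0·d))]² = 37.92, so 38 per arm and 76 in total.

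The corrected form matches the protocol exactly.

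**2. Reproducing the 92.**

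| Method | Total | Per arm |
|---|---|---|
| Add 20% of the evaluable number: 76 × 1.2 | 91.2, up to 92 | 45.6, up to 46 |
| Divide by (1 − 0.20): 76 / 0.8 | 95 | 47.5, up to 48 (96 in total) |

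Only the additive method gives 92, and 92 − 76 = 16 matches the head count in the sentence. Rounding cannot bridge 92 and 95.

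**3. What 92 delivers.**

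- A 20% loss: 92 × 0.8 = 73.6 in total and 46 × 0.8 = 36.8 per arm, against 76 and 38.
- Tolerated loss: 16/92 = 17.4%, which is 8/46 per arm.
- Nine losses in one arm are 9/46 = 19.6%, still under 20%, and leave 37.
- With 96 enrolled: 96 × 0.8 = 76.8, which is enough.

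**4. Effect on power.** Clustering is ignored, as in section 3.4. The continuity-corrected power comes from replacing n by n·(1 − 1/(n·d))² in the uncorrected formula. The Fisher power is a full enumeration, two-sided at 0.05.

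| Per arm | Corrected formula | Fisher's exact test |
|---|---|---|
| 38 | 80.1% | 83.2% |
| 37 (9 of 46 lost, 19.6%) | 78.8% | 81.8% |
| 36.8 (exactly 20% lost) | 78.5% | not an integer |
| 36 (10 of 46 lost, 21.7%) | 77.4% | 80.3% |

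**The case against.** The arithmetic is not in dispute. The case on the other side is that it does not matter.

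- **Power barely moves.** By Fisher's exact test it remains above 80% even with 10 of 46 lost per arm; only the conservative corrected formula falls below. This stands.
- **Enrolment is not controlled to within a few people.** Whole villages are taken in pairs, section 3.6 recruits every eligible villager, and section 3.9 permits replacement. With four villages tentatively planned (section 3.3), 92 means about 23 per village, so 92 and 96 may lead to the same villages. This stands as a reason why the practical effect may vanish. It does not make 92 and 20% consistent.
- **The 20% is a round guess without a cited basis,** and 17.4% is within its uncertainty. That is fair, and it is also why restating the percentage is acceptable.
- **The number takes no account of clustering,** so 96 is not a sound sample size either. That is a separate question. The present point concerns only the dropout step, and the same step will recur in any recomputation.
- **The wording is ambiguous.** The sentence mentions both Day 22 and three months. A 20% loss at each would need 76/0.64 = 118.75, so 119. The 16 people show that one 20% was applied, so a single cumulative loss is the natural reading, but the sponsor should confirm it.

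**Conclusion.** The figure is wrong as written. Enrolling 92 does not preserve 76 evaluable participants under a 20% dropout. It does so up to 17.4%. The shortfall against the stated assumption is 3 participants in total, or 4 with equal arms. At exactly 20% loss, power by the protocol's own type of calculation is 78.5% instead of 80.1%, about 1.6 points lower.

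This rests on a two-sided 5% test, on reading the 20% as one cumulative loss by Month 3, and on the individual-level calculation in section 3.4. The inconsistency is certain and its practical consequence is small. It should be corrected because it is a stated design figure that other sections use as a target.

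**What to change.** Change one sentence in section 3.4, in either of two ways:

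- **Keep the number:** state that 92 participants (46 per arm) allow for 17% cumulative dropout by Month 3. This needs no extra participants.
- **Keep the percentage:** state that 96 participants (48 per arm) allow for 20% cumulative dropout by Month 3. This means 4 more participants.

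The first is sufficient. In both cases the word cumulative is an addition that the sponsor should confirm, since the present sentence names two time points. If Figure 3.1 repeats the number, it should be aligned; the figure is not visible in the text available. Any later recomputation of the sample size, for whatever reason, should divide by one minus the dropout rate so that the same slip is not carried forward.

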3.5 Sampling and randomisation method

Prior to randomisation, matching of eligible Bajau villages will be carried out to increase precision and to minimise imbalance across intervention and control groups. This study involves 2 levels of randomisation. The randomisation sequence will be carried out by statistician employed at Faculty of Dentistry, Universiti Malaya.

At the first level of randomisation, all eligible Bajau villages from the total 39 Bajau villages will be paired according to location and average number of BQ chewers in the village (Figure 3.2).

At the second level of randomisation, computer generated random numbers will be used to randomly allocate the Bajau villages in each matched-pair to intervention and control groups. The match-pairs will be randomly selected until the sample size is met.

Bajau villages matched according to average number of BQ chewers in the village

Figure 3.2 Diagram depicting Flow of Matching of Clusters in the Study

